11.5.4. Efficacy

[figure not shown]
Weighted Means AUC (MMTT & Hyperglycemic Clamp Test)

- The weighted mean parameters will be derived by calculating the area under the curve (AUC) using the trapezoidal rule, and then dividing by the actual relevant time interval (i.e. $t_f - t_i$):

$$\text{Weighted Mean (t}_i\text{-t}_f\text{)} = \left[\frac{1}{2} \sum_{i=1}^{I-1} (t_{i+1} - t_i)(y_i + y_{i+1}) \right] / [t_f - t_i]$$

Where (example provided for MMTT AUC(0-120m):

- y_i = Value of endpoint at i^{th} time point
 - t_i = The i^{th} actual time point (mins) for MMTT:
 - Before MMTT : $t_1=0$
 - After MMTT : $t_2=15\text{m}$, $t_3=30\text{m}$, $t_4=60\text{m}$, $t_5=90\text{m}$, $t_6=120\text{m}$
 - t_f = Actual time point (hrs) of first non-missing obs (e.g. in planned time $t_f=0\text{h}$)
 - t_i = Actual time point (hrs) of last non-missing obs (e.g. in planned time $t_i=120\text{m}$)
 - I = Number of time points used in the AUC calculation (e.g. $I=6$)
- The examples provide details of how AUC's are calculated under certain scenario's and is to be adapted based on the study endpoints:

Weighted Means AUC (MMTT & Hyperglycemic Clamp Test)

Profile	Weighted Mean AUC Derivation
Complete	Area / Complete Time Interval
First Time Point Missing	Remaining Area / Remaining Time Interval
Last Time Point Missing	Remaining Area / Remaining Time interval
Time Point Missing Within Profile	Area using values of Remaining Profile / Complete Time Interval

Efficacy
Hyperglycemic Clamp Test: Calculation of Insulin Sensitivity Index (ISI)

➤ The ISI during the hyperglycemic phase (120-140 min) of the hyperglycemic clamp test (HCT) (DeFronzo et al, 1979) will be calculated as:
 $\text{ISI} = (M / I)_{120-140\text{min}} \times 100 \text{ (a)}$ 
➤ Ratio of glucose metabolized between 120 & 140 min (M expressed as mmol.kg⁻¹.min⁻¹) AND average insulin concentration between 120 & 140 min (I expressed as pmol/l), multiplied by 100.
 
➤ As the average insulin concentration is not directly available in the data, it will be replaced with the average C-peptide concentration instead.
 
➤ The glucose values taken for the derivation are those measured in the laboratory samples (LBSCAT = CLAMP), not the bedside glucose values (LBSCAT = BEDSIDE GLUCOSE).
 
➤ To correct for minor blood glucose fluctuations, M will be calculated as the average glucose infusion rate between 120 and 140 min minus a “space correction”.
 
➤ Parameter M & I will be derived as follows:
 <hr/> 
Parameter = M
 $M = \text{INF} - \text{SC} \text{ (b)}$ 
➤ M = Amount of glucose metabolized during the last 20 minutes (120-140 min) of the hyperglycemic phase of the HG clamp test.
 
➤ M expressed as mmol.kg⁻¹.min⁻¹.
 
➤ INF: Glucose infusion rate (mmol.kg⁻¹.min⁻¹).
 
➤ SC: Glucose space correction, amount of glucose necessary to fill the plasma glucose equivalent space (mg.kg⁻¹.min⁻¹):
 $\text{SC} = (G2 - G1) \times 0.095 \text{ (c)}$ 
✓ G2 and G1 are the glucose concentrations in milligrams per deciliter at the end and at the beginning of the time period.
 
✓ The value for SC needs to be converted to mmol.kg⁻¹.min⁻¹ before filling in (b).
 <hr/> 
Parameter = I
 
➤ Average C-peptide concentration during the same period (120-140 min) (expressed as pmol/l).
 <hr/> 
NOTES:
 
[1] Following review of the data for missing values, ISI may be calculated using the average C-peptide concentrations instead of average insulin concentrations between 120-140 min.
 
[2] Following review of the data, HOMA-2IR during HCT at following time points: -180 min (L180), -165 min (L165) and -150 min (L150) and during MMTT at time points: -10 min and 0 min (Matthews et al, 1985; Levy et al, 1998) may be also be calculated.

Efficacy
Mean Daily Insulin Use

➤ The mean daily insulin use in IU/kg will be derived as follow:
 
 1. Sum doses by participant and day to get daily dose in IU 2. Missing daily doses during the seven day space will be imputed with 0 3. Take the average and divide by the most recent available weight measurement to get mean daily insulin use in IU/kg
Responders (HbA1c)

 • A participant will be considered a responder if, at a given visit, the participant has: 
 ○ HbA1c $\leq 7.0\%$ and ○ Mean daily insulin use < 0.5 units/kg/day. • HbA1c and mean daily insulin use will be calculated as described above, and values compared at each time point of interest (Week 4, 8, 16, 28, 40, 52 and 64) to determine if a participant is classed as a responder or not
Partial Remission Status

 • A participant achieving partial remission status is defined as a participant with Insulin Dose Adjusted A1c (IDAA1C) ≤ 9.0 [3] • Insulin-dose adjusted A1c (IDAA1c) is a composite variable, which is a weighted sum of insulin use and HbA1c level. • IDAA1C is calculated as: 
 ○ HbA1c(%) + 4 x{mean daily insulin use per kg body weight (IU/kg)} ○ where the computation of mean total daily insulin use per kg body weight is as described above • The calculated IDAA1C value will be rounded to 2 decimal places before assigning partial remission status. Therefore the largest value assigned as ≤ 9.0 would be 9.004999.
C-peptide Responder

 • A participant is considered a C-peptide responder if there is $> -40\%$ change from baseline in C-peptide MMTT Weighted Mean AUC at 24 months (so participants with $>40\%$ loss in C-peptide are non-responders) [10] • Participants with missing C-peptide values at 24 months or baseline will have a missing C-peptide responder state. They will be reported as such in frequency tabulations, but not included in figures by C-peptide responder status. •

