6.7.3. Daily Insulin Use

Patients will be asked to record their daily insulin usage thoroughly and accurately for 7 consecutive days in a diary during the week before all outpatient visits or phone calls, ie, at Baseline, Day 14 and 21, Week 4 and 6 and Months 2, 3, 6, 9, 12, 18, 24, 36 (if applicable) and final follow up (if applicable). Information on insulin usage will be transcribed from diaries into the eCRF.

Mean daily insulin use over the 7 consecutive days (in units of IU per kg body weight per day) will be calculated for each patient at the timepoints described above.

Long acting and short acting insulin should be reported separately. The delivery device will also be recorded.

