9.1.4. Strategy for Intercurrent (Post-Randomization) Events

No imputation of missing data will be performed.

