9.1.5. Statistical Analyses / Methods

Details of the planned displays are provided in Section [11.10](#): List of Data Displays and will be based on GSK data standards and statistical principles.

Unless otherwise specified, endpoints / variables defined in Section [9.1.1](#) will be summarised using descriptive statistics, graphically presented (where appropriate) and listed.

Responder endpoints will be summarised only.

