11.2. Appendix 2: Assessment Windows

11.2.1. Definitions of Assessment Windows for Analyses

Analysis Set / Domain	Parameter (if applicable)	Target	Analysis Window		Analysis Timepoint
			Beginning Timepoint	Ending Timepoint	
All	All	Nominal Day	Nominal day – 1 days	Nominal day + 1 days	Visits for Day 14, Day 21 and Week 4 telephone call
All	All	Nominal Day	Nominal day –3 days	Nominal day +3 days	Visits from Week 6 to Month 3
All	All	Nominal Day	Nominal day –7 days	Nominal day +7 days	Visits from Month 6 to Month 24
Safety/PK/CD 3	All	In Window	-5 minutes predose	0 minutes predose	Predose
Safety/PK/CD 3	All	Nominal time point	Nominal time point	+5 minutes	Any postdose up to 6h
Safety/PK/CD 3	All	Nominal time point	Nominal time point	+10 minutes	Any postdose after 6h

Analysis Timepoint will be defined based on the nominal visit label, however a flag will be derived if a visit is considered outside of assessment window. Visits out of window will be included in all analyses but will be flagged in the listings. Sensitivity analyses may be performed excluding these visits.

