11.6.2. Handling of Missing Data

Element	Reporting Detail
General	
 Missing data occurs when any requested data is not provided, leading to blank fields on the collection instrument : 
 These data will be indicated by the use of a "blank" in participant listing displays. Unless all data for a specific visit are missing in which case the data is excluded from the table. Answers such as "Not applicable" and "Not evaluable" are not considered to be missing data and should be displayed as such.
Outliers	
 Any participants excluded from the summaries and/or statistical analyses will be documented along with the reason for exclusion in the clinical study report.

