		XXXX		X	xxx.x	xxx.x, xxx.x	xx.xx	xxx	xxx	Xxx
		XXXX		X	xxx.x	xxx.x, xxx.x	xx.xx	xxx	xxx	Xxx
ETC										

Programming Notes : [1] For applicable endpoints, include parameter as either a BY parameter or as first column in the table

Example : **EFF_T1 (Continued)**
Protocol : OTX116505
Population : Safety

Page 1 of X

Table X.XX

Summary Statistics (Absolute and Change from Baseline): C-Peptide & Glucose from Mixed Meal Tolerance Test

Summary: Change from Baseline

Please use same shell as for absolute values

Programming Notes :	[1] For applicable endpoints, include parameter as either a BY parameter or as first column in the table [2] If later it is decided to use log-transformation instead, then please use SAFE T-2 as template for them. [3]: If not all columns fit on one page, please switch to PD_T1 instead.
----------------------------	--

Example : EFF_T2
 Protocol : OTX116505
 Population : Safety

Table X.XX

Summary of Statistical Analysis (MMRM) Results of Change from Baseline: C-Peptide & Glucose Weighted Mean AUC(0-120 mins) from Mixed Meal Tolerance Test

Parameter:

Visit	Statistic	Placebo N=xx	OTX 9 mg N=xx	OTX 18 mg N=xx	OTX 27 mg N=xx
Month 3	n (1)	xx	xx	xx	xx
	n (2)	xx	xx	xx	xx
	LS Mean	x.xx	x.xx	x.xx	x.xx
	LS Mean Change	x.xx	x.xx	x.xx	x.xx
	Standard Error	x.xxx	x.xxx	x.xxx	x.xxx
	Difference from Placebo		x.xx	x.xx	x.xx
	95% Confidence Interval		x.xx - x.xx	x.xx - x.xx	x.xx - x.xx
P-value			0.xxx	0.xxx	0.xxx

Footnotes :	n(1) = Number of subjects in analysis; n(2) = Number of subjects with data at that visit P-value tests the null hypothesis of no difference from placebo.
Programming Notes	Use three decimal places for p-values. Always use ceiling instead of rounding (i.e. show 0.0501 as 0.051 and not 0.050. If the p-value is smaller than 0.001 display as "< 0.001".

Example : EFF_T3
 Protocol : OTX116505
 Population : Safety

Table X.XX
 Summary of Hypoglycaemic & Hyperglycaemic Events and Event Rates

Hypoglycaemic Events

Time Period Category	Placebo (N=xxx)			9mg (N=xxx)		
	n (%)	Number of Events / Mean [1]	Time Normalized Number of Events / Mean [2]	n/N (%)	Number of Events / Mean [1]	Time Normalized Number of Events / Mean [2]
Any Time Post-dose						
Number of Subjects	X			X		
Any Hypoglycemia	xxx (xx%)	xxx / xx.x	xxx / xx.x	xxx/xxx (xx%)	xxx / xx.x	xxx / xx.x
Hypoglycemia Grade 1	xxx (xx%)	xxx / xx.x	xxx / xx.x	xxx/xxx (xx%)	xxx / xx.x	xxx / xx.x

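### Unrecorded insulin-diary days are scored as 0 IU, which understates insulin use and can create false HbA1c responders and partial remitters; the responder week list also does not fit the trial's visits

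*SAP*

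**What the plan says.** Protocol 6.7.3: "Patients will be asked to record their daily insulin usage thoroughly and accurately for 7 consecutive days in a diary" before each visit or call. The mean over those seven days is expressed in IU per kg per day.

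SAP 11.5.4, Mean Daily Insulin Use, sums the doses for each day, applies the rule "Missing daily doses during the seven day space will be imputed with 0", then averages and divides by the latest weight. It sets no minimum number of recorded days.

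SAP 9.1.4, for efficacy: "No imputation of missing data will be performed". It states no exception. SAP 11.6.2: "Missing data occurs when any requested data is not provided, leading to blank fields on the collection instrument".

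The derived mean is used in three places:
- the MMRM of change from baseline in insulin use (SAP 9.1.5.1). The results shell EFF_T2 carries a p-value with the footnote "P-value tests the null hypothesis of no difference from placebo";
- the HbA1c responder rule: HbA1c at most 7.0% and insulin use below 0.5 units/kg/day;
- partial remission: IDAA1c, which is HbA1c plus 4 times insulin use, at most 9.0.

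For its timepoints the HbA1c responder rule has "values compared at each time point of interest (Week 4, 8, 16, 28, 40, 52 and 64"). SAP 11.2.1: "Analysis Timepoint will be defined based on the nominal visit label". After Week 6 the protocol's labels are Months 2, 3, 6, 9, 12, 18 and 24.

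**The concern.** A day the patient was asked to record and did not is missing data by the SAP's own definition. Scoring it as zero insulin is an imputation, and for a patient who injected that day it is a wrong value. The error at a visit has one sign: use is too low, and both glycaemic classifications move toward response. Read literally, a wholly blank week scores 0 IU/kg. At baseline that sits badly with SAP 5.2, where a missing baseline stays missing unless otherwise stated, and it makes the planned percentage change from baseline (Table 3.09) a division by zero.

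The rule is also out of step with the rest of SAP 11.5.4. A missing first or last AUC point is handled by dividing the remaining area by the remaining time, and a missing C-peptide value gives a missing responder status.

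By design there are 8 active patients per cohort, so one reclassified patient moves an arm's responder rate by 12.5 points (1/8). In a pooled placebo group of 6 (2 per cohort, if three cohorts filled) it is 16.7 points (1/6).

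The week list is a second, separate defect. A programmer cannot map it to this trial's visits without guessing, and it leaves out the last visit.

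**Working it through.** **The SAP's own figure.** SAP 11.5.4 gives 9.004999 as the largest IDAA1c that qualifies after rounding to two decimals. It rounds to 9.00 and qualifies; 9.005 rounds to 9.01 and does not. The figure is reproduced.

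**Classification.** For true mean dose d, constant over the week, and m unrecorded days:

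derived mean = d × (7 − m)/7; IDAA1c = HbA1c + 4 × derived mean.

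A patient not truly below 0.5 is scored below 0.5 when 0.50 ≤ d < 0.50 × 7/(7 − m). At HbA1c 7.0%, the largest true dose that qualifies for partial remission is (9.004999 − 7.0)/4 × 7/(7 − m).

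| Unrecorded days m | True dose passing the 0.5 rule (IU/kg/day) | Largest true dose for partial remission at HbA1c 7.0% |
|---|---|---|
| 0 | < 0.500 | 0.501 |
| 1 | < 0.583 | 0.585 |
| 2 | < 0.700 | 0.702 |
| 3 | < 0.875 | 0.877 |

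Examples at HbA1c 7.0%:
- d = 0.60, m = 0: IDAA1c 7.0 + 4 × 0.60 = 9.40. Neither class is met.
- d = 0.60, m = 1: 0.60 × 6/7 = 0.514; IDAA1c 9.06. Still neither.
- d = 0.60, m = 2: 0.60 × 5/7 = 0.429; IDAA1c 8.71. Both classes are met.
- d = 0.55, m = 1: 0.471; IDAA1c 8.89, against 0.55 and 9.20 from the recorded days. Both classes are met, wrongly.

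**Change from baseline.** At a constant 0.60 IU/kg/day the false change is 0.60 × (m at baseline − m at visit)/7. One missing day at the visit only gives −0.086; at baseline only, +0.086.

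For an assumed true arm difference of −0.20 (active 0.60 to 0.40, placebo constant at 0.60):
- one missing day everywhere: −0.20 × 6/7 = −0.171;
- at the active visit only: 0.40 × 6/7 − 0.60 = −0.257;
- at the placebo visit only: −0.20 + 0.086 = −0.114.

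Because the planned model adjusts for baseline, the direction was also checked by a large-sample ANCOVA simulation with one post-baseline visit. The assumed values, none from the documents, were baseline mean 0.5 and SD 0.15, slope 0.6 and residual SD 0.12 IU/kg, with on average one of seven days missing in the affected cell. With no true effect, the estimated difference was −0.071 (gaps in active, post-baseline), +0.072 (placebo, post-baseline), +0.041 (active, baseline) and −0.041 (placebo, baseline). With equal gaps everywhere, a true −0.10 became −0.087.

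**Week list.** Each listed week was compared with the nearest scheduled visit, using the windows in Protocol 6.1 (±1 day for the Week 4 call, ±3 for Week 6 to Month 3, ±7 for Months 6 to 24) and three month lengths. Entries are the nearest visit and the gap in days.

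| Week (day) | 30.4-day months | 30-day months | 28-day months |
|---|---|---|---|
| 4 (28) | Week 4: 0, in | Week 4: 0, in | Week 4: 0, in |
| 8 (56) | Month 2: 4.9, out | Month 2: 4, out | Month 2: 0, in |
| 16 (112) | Month 3: 20.7, out | Month 3: 22, out | Month 3: 28, out |
| 28 (196) | Month 6: 13.4, out | Month 6: 16, out | Month 6: 28, out |
| 40 (280) | Month 9: 6.1, in | Month 9: 10, out | Month 9: 28, out |
| 52 (364) | Month 12: 1.2, in | Month 12: 4, in | Month 12: 28, out |
| 64 (448) | Month 12: 82.8, out | Month 12: 88, out | Month 18: 56, out |

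Weeks 16, 28 and 64 match nothing under any month length. Week 4 matches a contact, but Protocol 6.2.2 describes it as a call or visit for adverse events, glycaemic events and medication, with no HbA1c evident, so the composite could not be scored there. Months 18 and 24 are absent.

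**The case against.** The best defence is that a blank day may be a true zero. The SAP lists insulin dose by dose (Listing 14, shell OTHER_L6). In such a log a day without insulin may have no row, and filling with 0 then restores the seven-day denominator that the protocol asks for. Patients off insulin are foreseeable: Protocol 1.2.5 reports 5% off insulin at one year in the teplizumab groups of an earlier phase III trial. This stands as far as it goes. Zero is right for those days, and averaging only recorded days would overstate their use: 0.30 IU/kg on five days and none on two is truly 0.30 × 5/7 = 0.214, not 0.30. But the SAP does not say how such a day is told apart from one the patient failed to record, and its rule covers both.

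SAP 9.1.4 can also be read as a visit-level statement under intercurrent events, with 11.5.4 as a specific derivation. That would soften the textual conflict, though 9.1.4 does not say so, and it would not make zero correct for an unrecorded day.

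The stakes are limited. The study tests no formal hypotheses, the two classifications are SAP additions to the protocol's endpoints, and SAP 9.1.5 says "Responder endpoints will be summarised only". All of this holds and bears on severity. It does not reach the insulin-use MMRM, which analyses a protocol secondary endpoint and reports p-values.

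On the week list, the rule is also worded per visit, and no biased result is shown to follow from the list. That is fair; it is a specification error that needs correcting.

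**Conclusion.** The concern holds and should be fixed before the analysis is run. Followed as written, the rule understates insulin use by one seventh per unrecorded day, for a constant dose and days on which insulin was taken. Patients near the cut-offs are then reclassified, always toward response: with HbA1c at or below 7.0%, true doses from 0.50 to just under 0.583, 0.70 or 0.875 IU/kg/day for one, two or three missing days. For change from baseline the sign depends on where the gaps fall, and equal gaps shrink a true difference.

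The actual effect cannot be stated, because neither document gives the rate of missing diary days by arm or visit, and the handling of insulin-free days on the eCRF is not described. With about 8 patients per dose, a few incomplete diaries could matter. The primary safety analysis is not affected.

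The week list is wrong for this trial whichever month length is used.

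**What to change.** 1. Score a day as 0 only where the diary or eCRF shows that no insulin was taken. Treat any other blank day as missing.
2. Average over the remaining days subject to a pre-specified minimum (4 of 7 is one possible choice). Below the minimum, or for a blank week, set insulin use, HbA1c responder status and partial remission status to missing, at baseline as at any other visit.
3. If the eCRF cannot separate insulin-free days from unrecorded ones, report both the zero-filled and the recorded-days versions, since they err in opposite directions.
4. Reconcile SAP 9.1.4 with 11.5.4, so that any within-visit rule is named as an exception.
5. Replace the week list in the HbA1c responder rule with the protocol visits at which HbA1c is measured, including Month 24, and align shell EFF_T4, which now shows a Week 4 row.

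The cost is SAP wording, a check of how the eCRF records insulin-free days, and a program change, with two versions if zeros cannot be identified. A few insulin values and classifications will become missing. No new data are needed.

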11.5.5. Pharmacodynamics

Target Engagement		
Overview of CD3 SAT/MOD Target Engagement Parameters		
The following parameters will be listed only:		
Parameter Category 1	LBTESTCD	LBTEST
CD3 SAT/MOD	CD4	CD4
CD3 SAT/MOD	CD4LY	CD4/Lymphocytes
CD3 SAT/MOD	CD8	CD8
CD3 SAT/MOD	CD8LY	CD8/Lymphocytes
CD3 SAT/MOD	MLYMP	Acquired Lymphocyte Events Mean
CD3 SAT/MOD	CD3EFS1	CD3e Free MESF(CD4+)
CD3 SAT/MOD	CD3EFS2	CD3e Free MESF(CD8+)
CD3 SAT/MOD	CD3EBS1	CD3e Bound MESF(CD4+)
CD3 SAT/MOD	CD3EBS2	CD3e Bound MESF(CD8+)
The following parameters will be summarised:		
CD3 SAT/MOD	CD3ER8	CD3e Copies/Cell(CD4+)
CD3 SAT/MOD	CD3ER9	CD3e Copies/Cell(CD8+)
CD3 SAT/MOD	CD3EFR8	CD3e Free Copies/Cell(CD4+)
CD3 SAT/MOD	CD3EFR9	CD3e Free Copies/Cell(CD8+)
CD3 SAT/MOD	CD3EBR8	CD3e Bound Copies/Cell(CD4+)
CD3 SAT/MOD	CD3EBR9	CD3e Bound Copies/Cell(CD8+)

Calculation of Target Engagement (%)		

The following formulas will be used to derive the Target Engagement percentage:
 $\text{Total Binding Sites} = \text{Occupied Binding Sites} + \text{Free Binding Sites} + \text{Down Modulated Binding Sites}$ 
In this equation, Total Binding Sites is not equal to the corresponding parameter shown above (e.g. CD3ER8 for CD4), except for the Baseline Visit. Instead, they differ by the number of Down Modulated Binding Sites, which is presumed to be zero at Baseline.
 
As the Total Binding Sites can be assumed to be approximately constant, the number of Down Modulated Binding Sites can be derived as follows:
 $\begin{aligned} \text{Down Modulated Binding Sites at Visit X} \\ = \text{Total Binding Sites at Baseline} - \text{Total Binding Sites at Visit X} \end{aligned}$ 
Therefore, percentage Target Engagement can be estimates as follows:
 $\text{Target Engagement (\%)} = \frac{\text{Occupied Binding Sites Visit X} + \text{Down Modulated Binding Sites Visit X}}{\text{Total Binding Sites at Baseline}} \times 100$ 
Target Engagement will be derived using 'Copies/Cell' for both CD4 and CD8, but not for MESF values, as the corresponding values have not been measured consistently across cohorts.
		
Derived Target Engagement (%) Parameters		
Parameter Category 1	Parameter Code	Parameter
CD3 SAT/MOD	CD4TE	Otelixizumab Down Modulation and Receptor Occupancy of CD3 ^{unicode epsilon} Target Sites on CD4
CD3 SAT/MOD	CD8TE	Otelixizumab Down Modulation and Receptor Occupancy of CD3 ^{unicode epsilon} Target Sites on CD8

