9.3.6. Pharmacodynamic/Biomarker Analyses

Descriptive statistics of both raw and change from baseline data, where appropriate, (i.e. n, arithmetic mean, standard deviation, minimum, median and maximum) will be calculated for pharmacodynamic/biomarker endpoints and summarized across cohorts. Graphical displays will be produced over time if deemed appropriate. All data will be listed.

If data permits, formal statistical analyses of efficacy endpoints may be conducted, if deemed appropriate and full details will be provided in the RAP. Based on the specified statistical analyses, estimates of the differences between doses of oteelixizumab and placebo will be calculated and appropriate statistical inferences based on these results will be made. Distributional assumptions underlying the analyses will be assessed as appropriate. If these assumptions are strongly violated, appropriate transformations will be investigated and if required alternative statistical analyses considered.

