Secondary Objectives (Pharmacodynamic)	Secondary Endpoints (Pharmacodynamic)

 To assess the effect of a single course of otelixizumab treatment on the time course and magnitude of CD4+ and CD8+ cells and CD3 binding and saturation on all these cells during repeat dose administration of otelixizumab 	
 Relative change from baseline (%) in CD4+ and CD8+ cells, free CD3 and bound otelixizumab on CD4+ and CD8+ cells on Days 1 through 14.

over 14 days in NOT1DM patients.	

 To assess the effect of a single course of otelexizumab treatment on the immunogenicity of otelexizumab in NOT1DM patients. 	
 Change from baseline in anti-drug antibody levels at Months 3 and 6.
Exploratory Objectives *	Exploratory Endpoints *

 To assess the effect of a single course of otelexizumab treatment on circulating lymphocyte populations over 24 months in NOT1DM patients. 	
 Change from baseline in absolute lymphocyte counts and ratios in some or all, but not limited to subsets (CD3+ CD4+, CD3+ CD8+, and CD19+ cells) and phenotype (e.g. effector, memory, regulatory T cells, e.g. CD45RA, CCR7+) over Week 6 to Month 24.

 To assess the effect of a single course of otelexizumab treatment on circulating lymphocytes such as regulatory T cell numbers (as quantified by CD3 and demethylated FoxP3 expression) and Th17 cells over 24 months in NOT1DM patients. 	
 Change from baseline in cell-type specific methylation marker expression in some or all, but not limited to CD3, FoxP3 and Th17 in whole blood over Week 6 to Month 24.

 To assess the effect of a single course of otelexizumab treatment on absolute numbers and ratios of circulating antigen specific CD8+ T cells over 24 months in HLA-A2+ NOT1DM patients. 	
 Change from baseline in absolute numbers and ratios of HLA-A2-restricted CD8 T lymphocytes reactive to specific auto-antigens (by multimer) over Week 6 to Month 24.

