9.2. Overview of Planned Pharmacodynamic Analyses

9.2.1. Endpoints / Variables

The following endpoints will be analysed:

- Relative change from baseline (%) in CD4+ and CD8+ cells, free CD3 and bound oteelixumab on CD4+ and CD8+ cells on Days 1 through 14.

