9.2.5. Statistical Analyses / Methods

Analysis will be restricted to summary statistics. Details of the planned displays are provided in Section [11.10](#) List of Data Displays and will be based on GSK data standards and statistical principles.

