
 EBV Viral Load (EBVPCR_B): 
 Viral Load will also be categorized, using these groups: 
 0-1000 copies/10⁶PBM cells >1000-10000 copies/10⁶PBM cells >10000-100000 copies/10⁶PBM cells >100000 copies/10⁶PBM cells The same rules as for laboratory parameters will be applied for BLQ/ALQ values. 
Any viral load given as > XX.X or < XX.X will be treated in the same manner as described for laboratory parameters. If the result is given as not detected, then it will be imputed as 1 copies/10⁶PBM cells instead.
				

Auto-Antibodies

Positive/Negative results will be derived for all the auto-antibodies, where positive is defined as:
 
 antibody to glutamic acid decarboxylase (anti-GAD) ≥ 2.6% binding antibody to protein tyrosine phosphatase-like protein (anti IA 2) ≥ 0.44% binding Qualitative status (positive/negative status) is directly provided for islet cell antigen and will be used ZnT8 Autoantibody ≥ 1.02% binding IAA ≥ 0.6% binding 
In addition, the number of positive results at Screening (with the exception of IAA) will be derived in ADSL.

Immunogenicity

The presence of anti-drug antibodies will be summarized by positive/negative status at each time point. A participant is considered positive at a specific time point if both the Screening and the Confirming sample is positive.

The listing will show individual results for the Screening, Confirming and Titer tests. Not applicable tests will be omitted from the listing.

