11.10.9. Pharmacodynamic Tables

Pharmacodynamic : Tables					
No.	Population	IDSL / TST ID / Example Shell	Title	Programming Notes	Deliverable [Priority]
Pharmacodynamic					
4.01.	Safety	Non- Standard PD_T1	Summary Statistics (Absolute and Change from Baseline): Target Engagement	For parameters with imputation please also include no. of subjects with LLQs & ULQ. Include the parameters to be summarized from 11.5.5 and also show the two derived % Target Engagement variables	FA (SAC)

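### The Day 1 to 14 change in CD4+ and CD8+ cells is a secondary endpoint that the SAP names for analysis but then only lists, so no by-treatment summary is produced

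*SAP*

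**What the plan says.** Protocol Section 2 and SAP 2.2 state the first secondary pharmacodynamic endpoint as "Relative change from baseline (%) in CD4+ and CD8+ cells, free CD3 and bound otelixizumab", measured on Days 1 through 14. The matching objective asks for the time course and magnitude of CD4+ and CD8+ cells as well as CD3 binding. SAP 9.2.1 repeats the endpoint among those to be analysed ("Relative change from baseline (%) in CD4+ and CD8+ cells, free CD3 and bound"), and SAP 9.2.5 sets the method: "Analysis will be restricted to summary statistics". Protocol 9.3.6 says that descriptive statistics, raw and change from baseline where appropriate, "will be calculated for pharmacodynamic/biomarker endpoints and summarized across cohorts".

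SAP 11.5.5 splits the CD3 SAT/MOD panel in two. CD4, CD4/Lymphocytes, CD8 and CD8/Lymphocytes fall under "The following parameters will be listed only". The summarised group holds six CD3e copies-per-cell parameters: total, free and bound, each on CD4+ and CD8+ cells. Table 4.01, titled "Summary Statistics (Absolute and Change from Baseline): Target Engagement", takes the summarised group plus the two target engagement percentages. Figure 4.01 shows the same parameters as the table.

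The other secondary endpoint in this block is "Change from baseline in anti-drug antibody levels at Months 3 and 6". For it, SAP 11.5.3 says: "The presence of anti-drug antibodies will be summarized by positive/negative status at each time point". Titres go to a listing.

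**The concern.** An endpoint that both documents state, and that the SAP says it will analyse, loses two of its four parts between the methods section and the list of displays. CD4+ and CD8+ cell numbers over the dosing period are the part that shows how the two T-cell subsets move with dose. This is a dose-escalation study whose own risk table (Protocol 3.4) says that lymphopenia increases with daily dose. As the displays stand, a reader of the report who wanted the subset time course by treatment group would have to compute it from subject listings.

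The change is also undeclared. Protocol 9.3.2 requires departures from the planned analysis to be documented in the RAP, and SAP 2.1 states that there are none.

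**Working it through.** No arithmetic on sample size or error rates applies. The check traces each part of the two endpoints to its displays.

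| Quantity | Summary table | Figure | Listing |
|---|---|---|---|
| CD4+ cells, Days 1-14 | none | none | 46 (absolute and change) |
| CD8+ cells, Days 1-14 | none | none | 46 (absolute and change) |
| Free CD3 on CD4+/CD8+ | 4.01 | 4.01 | 46 |
| Bound drug on CD4+/CD8+ | 4.01 | 4.01 | 46 |
| Anti-drug antibody status | 2.22 | none | 38 |
| Anti-drug antibody level (titre) | none | none | 38 (no change column) |

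**Could another display fill the CD4/CD8 gap?** Table 5.01 summarises CD4 and CD8 by flow cytometry. Protocol 6.6.4 samples that assay at Day -1 and Months 1.5, 3, 6, 12 and 24; only TCR sequencing has a Day 6 sample. Table 5.01 therefore has no post-dose value within Days 1 to 14.

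**Is lymphocyte loss itself unreported?** No. Lymphocytes are a haematology parameter (Protocol 6.4.4.1). Protocol 6.2.2 draws haematology on Day -1, Days 2 to 6 (pre-dose), Day 14 and Day 21. Tables 2.13, 2.14 and 2.15 give values, changes from baseline and worst-case shifts. Only the CD4/CD8 split is absent.

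**Is a percent change in free CD3 missing?** Largely not. In SAP 11.5.5, measured total sites are occupied plus free, and down-modulated sites at visit X are the baseline total minus the measured total at X. So

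Target Engagement = [Occ(X) + Total(base) − Occ(X) − Free(X)] / Total(base) = 1 − Free(X)/Total(base).

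If no drug is bound before the first dose (an assumption), Total(base) = Free(base). Target Engagement (%) is then the percent fall in free CD3. Table 4.01 shows it for both cell types, so no separate request is needed.

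**Can counts be derived if the panel reports raw events?** SAP 11.5.5 gives no units for CD4 and CD8 in this panel. The natural fallback is same-day lymphocytes × subset percentage / 100. It needs haematology at the same time:
- Day 1: pharmacodynamic samples before dosing and from 30 minutes to 16 hours after the start of infusion, but no haematology. Counts are not derivable.
- Days 2 to 6, pre-dose: both are drawn. Derivable.
- Day 6, 1 hour: haematology is pre-dose only. Not derivable.
- Day 14: both are drawn. Derivable.

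The fallback therefore gives no same-day Day 1 baseline and no Day 1 time course.

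**The case against.** The best defence is that listing was deliberate. SAP 9.2.2 says it is the target engagement variables that will be summarised, and the protocol's promise of descriptive statistics carries a where-appropriate qualifier. The study tests no formal hypotheses, every subject's CD4 and CD8 values and changes are in Listing 46, and total lymphocytes are tabulated. This shows that the choice may be intended. It does not remove the conflict between 9.2.1 on one side and 9.2.2 and 11.5.5 on the other, and it does not explain why SAP 2.1 reports no departure. The SAP gives reasons elsewhere: MESF values were not measured consistently across cohorts, and some exploratory biomarkers are listed for data quality. It gives none for these four parameters.

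A reader might infer more than the documents support:
- That two whole secondary endpoints go unsummarised. The CD4+/CD8+ cells are one component of a compound endpoint whose free and bound CD3 components are summarised. Antibody status is tabulated by visit, and the shell used for Table 2.22 would also count new positives and reversions.
- That the report would hold no estimate of lymphocyte loss by dose. Tables 2.13 to 2.15 provide one for total lymphocytes.

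On antibodies, the defence is fair. Protocol 6.6.1 describes an assay for presence, and in groups of about eight, status counts plus individual titres lose little. Few confirmed positives may exist.

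**Conclusion.** The point holds for the CD4+ and CD8+ cell component on Days 1 to 14. Two of the four quantities in the first secondary pharmacodynamic endpoint have no summary table and no figure on any of the seven sampling days, and the SAP contradicts its own 9.2.1 without declaring it. The loss is the subset time course by treatment group. Total lymphocytes and CD3 binding are unaffected, and so is the conduct of the trial.

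The antibody point is secondary. The endpoint is worded as a change in level and the only table gives status, but the practical loss is small.

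The coverage finding needs no outside figure. The statement that Target Engagement (%) stands in for percent change in free CD3 assumes no bound drug before the first dose. Whether the panel's CD4 and CD8 values are counts or raw events cannot be settled from the documents.

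**What to change.** 1. In SAP 11.5.5, move CD4, CD4/Lymphocytes, CD8 and CD8/Lymphocytes to the summarised group. Add them to Table 4.01 and Figure 4.01 for Days 1 to 14, with percent change from baseline named explicitly, as the SAP already does for insulin use in Table 3.09. Align SAP 9.2.2 with 9.2.1.
2. If the CD4 and CD8 values prove to be raw events, summarise the two percentages at all times. Derive counts only at pre-dose Days 2 to 6 and at Day 14, and do not present a same-day Day 1 baseline for them.
3. If there is a reason to keep these parameters in listings, state it and record the departure in SAP 2.1.
4. Optional: add titre (n, median, range) among confirmed positives at Day -1 and Months 3 and 6 to Table 2.22, or declare in SAP 2.1 that level has been replaced by status.

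The cost of items 1 and 4 is extra rows and panels in existing displays, from data already collected. Item 2 adds a derivation, and only if the units require it.
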